3.8. Data analysis plan

3.8a. Overview: Below we provide an overview of the study design considerations, and the analysis plan for each aim. We first present the approach for Aim 1, which involves traditional between-groups comparisons. Given the comparative effective approach required by Aims 2 and 3, we discuss these separately, and provide details regarding the structure of hypothesis testing for this method. In particular, we focus on the null hypothesis testing procedure and the determination of the clinically-meaningful effects (i.e., delta or δ) to be considered with respect to non-inferiority.

3.8b. Study Design Considerations: The equivalency of the two treatment groups at baseline is produced by the random assignment to groups. Randomization (combined with the ITT analysis strategy) should produce groups that differ only by chance with respect not only to factors related to study outcomes, and also to the outcomes themselves. Nevertheless, the adequacy of the randomization will be assessed by comparing the groups across outcomes measured at baseline. We will use a stratification based on hours of sleep reported on the postal survey (>6 versus ≤ 6 hours) to assign participants to strata for randomization. We have chosen stratified randomization to further increase the likelihood that the groups will be equivalent at baseline. The inclusion of covariates in such a situation would not be for the purpose of ensuring the comparability of the groups (because that comparability is created via randomization), but covariates may be used to enhance statistical power by reducing error variance.

We anticipate that some participants will not complete the intervention; however, we will continue to collect post-treatment and 3-month follow-up data, regardless of whether they complete the intervention program. Participants will be offered monetary incentives for providing post-treatment and follow-up assessments, regardless of whether they complete the intervention program to which they were assigned. We anticipate this will maximize the completeness of data; however, some data loss is unavoidable. In our recent study of older Veterans, we were able to obtain follow-up data for up to one year in 90% of randomized participants.

To preserve the equivalency formed by randomization of participants to the intervention and control groups, intent-to-treat (ITT) analyses will be used including all randomized participants for hypothesis testing. ITT analysis requires complete data, so missing data will be imputed. If imputation is necessary, we will use multiple imputations. These results will be compared to an “as treated” analysis where only those with complete data will be analyzed, thus no imputations will be required. We will use this approach since the “as treated” has the benefit of not imputing any data, but also has the drawback of not analyzing all participants as randomized and therefore the potential for introducing bias into the results.

3.8c: Data Analysis for Aim 1:

Testing of Hypothesis 1, that participants in the ABC-I program will be less likely to discontinue treatment and will show better adherence to behavioral recommendations than participants in the CBT-I program) will involve a series of statistical comparisons between the ABC-I and CBT-I groups. To test whether the participants in ABC-I are less likely to discontinue treatment, the percentage who dropout in the ABC-I group will be compared to the percentage who dropout in the CBT-I group. This comparison will be made using a two-by-two χ^2 test of whether dropping out (1=yes 0=no) is independent of treatment group assignment (1=ABC-I, 2=CBT-I). To compare measures of adherence to behavioral recommendations (based on electronically time-stamped sleep diary data), a two group t-test will be used. The main variables of interest will be the minutes of deviation from the assigned earliest bedtime and latest rise time for each session. We will calculate the mean number of minutes the participant goes to bed in advance of their scheduled bedtime and the mean number of minutes they get up later than their scheduled rise time (note that going to bed later than the assigned time or getting up earlier than the assigned time is consistent with the recommendations and is not considered non-adherence). We will then compute the mean minutes of deviation for each participant. We

will also compare rates of adherence to other between-session activities, and a percent of days the activity was conducted will be computed for each participant.

Sample Size Calculations: To assess the power for Aim 1, we considered preliminary data gathered using the proposed intervention and previously published research. To estimate the power to compare dropout rates for each of the two groups, we used our preliminary data and published studies of ACT-based interventions and CBT-I.^{17;18;84-87} Based on those sources, we conservatively anticipate the dropout rate for ABC-I will be 22% compared to 45% for CBT-I. **Table 11** shows the required sample size to detect this difference (n=178) and other potential differences. The rows show dropout rates for ABC-I ranging from 16% to 28%, and the columns show dropout rates for CBT-I, ranging from 39% to 51%. Each cell shows the total N (for the two groups combined). The current study would need 148 subjects (74 per group) to have 80% power to detect a difference in dropout rates as found in the previous research.

Aim 1 also addresses differences between ABC-I and CBT-I in adherence to sleep restriction and stimulus control recommendations. Again, based on previously-published studies^{17;18;84-87} and our own preliminary data, we estimate that participants who complete the CBT-I intervention will deviate from their recommended bed time by an average of 29 minutes (SD=36 minutes) per night, while participants in the ABC-I program will deviate from their recommended bed time by an average of 9 minutes (SD=19 minutes). To detect a difference of this size with 80% power, we would require a total of 66 participants (33 per group). Similarly, we anticipate that individuals in the CBT-I group will deviate from their recommended rise time by 36 minutes (SD=40 minutes), while individuals in the ABC-I program will deviate from their recommended rise time by only 6 minutes (SD=14 minutes). To detect a difference of this magnitude with 80% power would require a total of 32 observations (16 per group). Using the proposed sample size required to detect a difference in dropout rates (n=148) we will have ample statistical power to detect differences in adherence.

Table 11: Sample size to detect differential dropout rates between CBT-I and ABC-I. N=148 (74 per group) is adequate to measure the expected difference. Other measurable differences with N=148 are shown in **bold**.

ABC-I Dropout rate	CBT-I dropout rate						
	39%	41%	43%	45%	47%	49%	51%
16%	134	116	102	90	82	74	66
18%	162	138	120	106	94	84	76
20%	200	168	144	124	108	96	86
22%	252	206	174	148	128	112	98
24%	326	260	212	178	152	130	114
26%	436	336	268	218	182	154	134
28%	612	448	344	274	224	186	158

3.8d: Data analysis for Aims 2 and 3 (Hypothesis 2: ABC-I and CBT-I will be similarly effective in improving self-reported and objectively measured sleep from baseline to post-treatment; Hypothesis 3: ABC-I and CBT-I will be similarly effective in improving self-reported and objectively measured sleep from baseline to 3-months follow-up).

Two Step Hypothesis Testing of Non-inferiority: Hypotheses 2 and 3 seek to show that ABC-I is not inferior to CBT-I in terms of treatment effects (i.e., changes in sleep quality). Non-inferiority is established by framing the null

hypotheses in terms of the difference between the treatment means and comparing this difference to a pre-specified value, delta (δ), which represents the equivalence margin.

Determination of delta (δ): We elected to use a value of δ equivalent to an effect size of $d=0.40$. (i.e., 4/10ths SD). With respect to ISI, this represents a 2 point difference between the treatment effects. For PSQI, this represents a 1.4 point difference, and for actigraphically-estimated sleep percent, a difference of 5%.

Description of analysis: With respect to this study, non-inferiority is established by showing that the efficacy of ABC-I is no more than δ units less than CBT-I (**Table 12**).⁸⁸ This is tested by formulating a one sided null hypothesis that the difference between CBT-I and ABC-I is greater than or equal to δ (i.e., $H_0: \mu_{CBT-I} - \mu_{ABC-I} \geq \delta$) against the alternative hypothesis that the difference is less than δ (i.e., $H_A: \mu_{CBT-I} - \mu_{ABC-I} < \delta$). If the null

[figure not shown]
Table 12: Hypothesis testing in a non-inferiority study comparing ABC-I to CBT-I.

Type of study	Hypotheses	
	Null hypothesis (H_0)	Research Hypothesis (H_1)
Traditional comparative study	There is no difference between ABC-I and CBT-I	There is a difference between ABC-I and CBT-I
Non-inferiority study	ABC-I is inferior to CBT-I	ABC-I is not inferior to CBT-I (H₂ and H₃)

hypothesis is rejected, then the non-inferiority of ABC-I is established. For Aims 2 and 3, this two step process avoids the pitfall of erroneously interpreting a failure to reject the null hypothesis as evidence of no difference

between the treatment groups. **Figure 8** illustrates four hypothetical patterns of results with respect to the outcome ISI using $\delta = 2$. In **Result 1**, the mean of CBT-I is greater than ABC-I and the confidence interval of this difference includes δ , and the noninferiority of ABC-I is not established. In **Result 2**, the mean of CBT-I is greater than ABC-I, however, the confidence interval excludes δ and the noninferiority of ABC-I is established. **Result 3** shows that the mean of ABC-I is greater than CBT-I and the confidence interval excludes δ , establishing the non-inferiority of CBT-I. **Result 4** shows that the mean of ABC-I is greater than the mean of CBT-I, however, the confidence interval includes δ so the noninferiority of ABC-I is not established.

Figure 8: Depiction of possible results for non-inferiority testing of ABC-I compared to CBT-I. The figure shows mean differences and 95% CI.

Statistical Analysis: To conduct the non-inferiority tests of Hypotheses 2 and 3, we will first use a 2 (group) by 3 (time) mixed model analysis of variance (ANOVA). The ABC-I vs. CBT-I groups will form the 2-level between groups factor, and the 3 time points (baseline, post-treatment, follow-up) will form the within groups factor. The null hypothesis will be that the differences between groups are greater than or equal to delta, as specified above, for ISI (2 points), PSQI (1.8 points) and sleep percent (5%).

Hypothesis 2 will compare the impact of the ABC-I to CBT-I at post-treatment (as compared to baseline) in terms of self-reported (ISI total score and PSQI total score) and objectively-measured (actigraphically-measured nighttime percent sleep) sleep quality variables. For each outcome measure, a 2 (group) by 3 (time) mixed model analysis of variance (ANOVA) will be performed. To directly test the impact of ABC-I vs. CBT-I on the change in outcomes from baseline to post-treatment, a planned interaction comparison will be tested that crosses treatment group (ABC-I vs. CBT-I) with time using a 1-1-0 contrast for the time factor). This interaction comparison will be used to directly test this hypothesis, that the ABC-I group shows greater positive changes (from baseline to post-treatment) on the outcome measures as compared to the CBT-I group.

Hypothesis 3 will explore whether improvements seen at post-treatment are maintained over a 3-month follow-up time period. As with hypothesis 2, for each outcome measure, a 2 (group) by 3 (time) between/within analysis of variance (ANOVA) will be performed, but two interaction contrasts will be examined. The primary contrast of interest will examine impact of ABC-I (compared to CBT-I) on the change from baseline to 3 month follow-up by applying a -1 0 1 contrast to time and interacting that with treatment group. This interaction contrast will assess the impact of the ABC-I (compared to CBT-I) from baseline to the 3 month follow-up, assessing the persistence of the treatment effects. A secondary contrast will examine the change from post-treatment to six month follow-up by applying a 0 -1 1 contrast on time and interacting that with treatment group. This secondary comparison will assess differences in changes from post-treatment to 3 month follow-up for the ABC-I and CBT-I groups. Conceptually, this second contract will test whether there is either continued improvement after post-treatment (i.e., sleep is better at 3 months follow-up compared to post-treatment, or whether there is relapse (i.e., sleep is worse at 3 months follow-up compared to post-treatment).

Sample Size Calculations: For Aims 2 and 3, the required sample size was determined based on the minimum clinically-meaningful difference between the two treatments, rather than on the estimated effect size for an active treatment versus control condition. This non-traditional approach is required for comparative effectiveness designs.⁸⁸ To develop estimates of clinically-meaningful differences between treatments, we examined studies of CBT-I in the published literature.⁸⁹⁻⁹¹ We then considered clinically meaningful changes in ISI and PSQI scores and in objectively-measured sleep percent. We determined that a difference between the two treatment groups of more than 2 points on the ISI or PSQI, or more than 5% in objectively-measured sleep percent would constitute a clinically-meaningful difference between the treatments. This represents an effect size of approximately $d=0.40$ (that is, 4/10s of a standard deviation for each outcome measure). The required sample size (with alpha=.05 and .80 power) to detect for an effect size of 0.40 is n=138. We plan to randomize

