3. RESEARCH DESIGN AND METHODS

3.1. Basic Study Design

The proposed study is a 4-year randomized trial to test the effectiveness of a novel treatment program for insomnia among women Veterans receiving outpatient care. The basic design is shown in **Figure 7**. As in our prior work, we will identify potential participants using a postal screening survey, including questions targeting ICSD diagnostic criteria for insomnia.⁴⁶ This survey will be sent to women who have received outpatient care (at least one visit) at the VA Greater Los Angeles Healthcare System (VAGLAHS) within the prior six months and live within a 50 mile radius of the Sepulveda Ambulatory Care Center (SACC) where the study will be conducted. Those who return the survey indicating symptoms of insomnia will be contacted by telephone to clarify study eligibility and to invite them for in-person screening/enrollment and baseline assessments. We anticipate enrolling a total of 400 women to achieve the proposed sample of 148 randomized participants (74 to receive ABC-I, and 74 to receive CBT-I).

[figure not shown]
Participants will complete a comprehensive sleep, mental health and physical health assessment at baseline (pre-treatment), immediately after the intervention ends (post-treatment), and 3 months after the end of the intervention (3-month follow-up). The primary outcomes will focus on differences in treatment adherence and attrition. We will also compare the effectiveness of the two interventions in terms of improving self-reported sleep quality and insomnia symptoms, plus objectively monitored sleep/wake patterns (wrist actigraphy) measured at post-treatment and at the 3 month follow-up using a non-inferiority design. Data will be analyzed both for treatment completers and for all randomized participants in an intention to treat analysis. Based on our recent work in this area, we expect to be able to enroll and randomize 148 women Veterans into the study within the proposed time frame. The planned research has been informed by our recently-completed HSR&D funded pilot study,⁴⁶ and our ongoing HSR&D funded intervention trial of CBT-I with older Veterans (PI: [name]).

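### Aim 1 makes attrition and adherence jointly primary but tests them separately, with no error control and no rule for a mixed result; three tests at .05 carry about a 14% family-wise error rate

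*Combined protocol and SAP*

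**What the plan says.** Section 3.1 names two primary outcomes without ranking them: "The primary outcomes will focus on differences in treatment adherence and attrition".

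Section 3.8c states Hypothesis 1 as a joint claim, that ABC-I participants will be "less likely to discontinue treatment and will show better adherence to behavioral recommendations". Testing it "will involve a series of statistical comparisons between the ABC-I and CBT-I groups", which are then listed one by one:

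- Dropout: "the percentage who dropout in the ABC-I group will be compared to the percentage who dropout in the CBT-I group", by a two-by-two chi-square test.
- Adherence to the sleep schedule, by t-test: "The main variables of interest will be the minutes of deviation from the assigned earliest bedtime and latest rise time for each session".
- Further comparisons, number not given: the team "will also compare rates of adherence to other between-session activities".

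The sample-size text in 3.8c sizes three comparisons separately, each at 80% power: dropout (148 in total), bedtime deviation (66) and rise-time deviation (32).

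The only stated significance level is in 3.8d, for Aims 2 and 3: "The required sample size (with alpha=.05 and .80 power) to detect for an effect size of 0.40 is n=138". No section gives a multiplicity adjustment, a testing order, a single primary endpoint for Aim 1, or a rule that every part of Hypothesis 1 must succeed.

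**The concern.** When several tests serve one primary aim and no rule links them, the false-positive rate for the aim as a whole exceeds the level of each test. A mixed result, such as a difference in rise time but not in dropout, also has no agreed reading. It could be reported as success on a primary outcome or as failure of the hypothesis, and the choice would be made after the data are seen. What is at stake is how a claim on the trial's primary aim should be weighed.

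**Working it through.** **Step 1. Which level does Aim 1 use?** Section 3.8c does not say, so I checked which level reproduces its sample sizes.

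*Dropout, 22% vs 45%, 80% power, two-sided .05.* The mean proportion is 0.335 and the difference 0.23.

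n = [1.960·√(2·0.335·0.665) + 0.842·√(0.22·0.78 + 0.45·0.55)]² / 0.23² = (1.308 + 0.545)² / 0.0529 = 64.9, or 65 per group (130 in total).

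With continuity correction: n' = (64.9/4)·[1 + √(1 + 4/(64.9·0.23))]² = 73.4, or 74 per group. This is the plan's 148. A one-sided .05 test with the same correction gives 60 per group (120 in total), which does not match.

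The text of 3.8c also prints 178 beside these rates. That is the Table 11 cell for 24% vs 45% (89 per group); the cell for 22% vs 45% is 148.

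*Bedtime, 29 vs 9 minutes, SDs 36 and 19.* Mean variance = (1296 + 361)/2 = 828.5. n = 2·(1.960 + 0.842)²·828.5/20² = 32.5, or 33 per group (66 in total).

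*Rise time, 36 vs 6 minutes, SDs 40 and 14.* Mean variance = (1600 + 196)/2 = 898. n = 2·(1.960 + 0.842)²·898/30² = 15.7, or 16 per group (32 in total).

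All three figures reproduce at two-sided .05 for each test, with no allowance for multiplicity.

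**Step 2. Family-wise error when all nulls are true.**

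- Three independent tests: 1 − 0.95³ = 14.3%.
- Only the two adherence tests correlated (simulated): 14.0% at 0.3, 13.6% at 0.5, 12.9% at 0.7, 11.7% at 0.9.
- All three correlated (simulated): 13.6% at 0.3, 12.5% at 0.5, 10.9% at 0.7, 8.4% at 0.9.
- Only false claims favouring ABC-I, independent tests: 1 − 0.975³ = 7.3%, against 2.5% for one test.
- Adherence as one combined test: 1 − 0.95² = 9.8%.
- A fourth independent test from the other activities: 1 − 0.95⁴ = 18.5%.

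The documents give no correlations, so these are an assumed range.

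**Step 3. What Holm does.** The smallest of the three p-values is compared with .05/3, the next with .05/2 and the largest with .05, stopping at the first failure. With all nulls true (dropout 33.5% in both arms), simulated family-wise error fell from 13.7–14.4% to 4.8–4.9%.

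**Step 4. What Holm costs.** The simulations used 200,000 trials per scenario and the continuity-corrected dropout test. Dropout was taken as independent of adherence, and the two adherence tests were correlated 0 or 0.5. Adherence was analysed either in all 74 per arm or in expected completers: 74·0.78 ≈ 58 on ABC-I and 74·0.55 ≈ 41 on CBT-I.

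| True adherence effects | Adherence data (ABC-I/CBT-I) | Dropout power, unadjusted | Dropout power, Holm |
|---|---|---|---|
| As planned | 74/74 | about 80.4% | about 80.2% |
| As planned | 58/41 | about 80.4% | about 78.6–79% |
| Half as large | 74/74 | about 80.5% | about 74.0–74.2% |
| Half as large | 58/41 | about 80.4% | about 70.9–71.2% |
| Null | either | about 80.5% | about 67.0–67.2% |

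At the planned effects, bedtime power falls from 98.8% to about 98.4% (74/74) or from 90.2% to about 88.4% (58/41). Rise-time power stays above 99%. Without the continuity correction, dropout power starts near 85% and its losses are similar: 5.5 to 8.5 points at half effects and about 12.5 points at null effects.

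**The case against.** The strongest reply is that Hypothesis 1 joins its two parts with an "and". If dropout and every adherence test had to succeed, supporting the hypothesis would carry no family-wise inflation, and a result on rise time alone would simply mean that it was not supported. That reading is open, but the rule is not written, and section 3.8c describes separate comparisons with nothing to combine them. Conversely, a reader might infer that the plan licenses any single significant comparison as a positive primary result. The documents do not say that either. The defect is that neither rule is stated.

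Second, dropout can be seen as the lead outcome. It set the sample size, and section 3.5b classes the deviation minutes as process variables. That suggests priority, but 3.5b calls completion versus dropout only one among the main outcomes, and 3.1 makes adherence primary alongside attrition.

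Third, the number of tests is uncertain. Section 3.8c speaks of one t-test and of averaging deviation minutes within each participant, which could mean a single adherence test. Separate sizing of bedtime and rise time makes three the more natural count, and two tests still give 9.8%. In the other direction, the mention of each session might suggest 2 × 5 + 1 = 11 tests and up to 43% error if independent. The averaging step argues against that, so I do not rely on it.

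**Conclusion.** The point stands: the primary aim has several tests, no error control and no rule for a mixed result. The figure of about 14% rests on three tests, each at an inferred two-sided .05, with all nulls true, low to moderate correlation, and errors in both directions counted. It should not be read as the chance of wrongly favouring ABC-I, which is about 7%. High correlation lowers the 14%, but every case examined stays above the level of a single test.

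Two further inferences about the remedy would go too far. Holm does not remove false positives; it caps the family-wise rate at 5%. Nor is it nearly free in general. The small cost holds only if the adherence effects are close to those planned. Even then, dropout power can slip just below the 80% target if only completers contribute adherence data.

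**What to change.** In section 3.8c, name dropout, bedtime deviation and rise-time deviation as the confirmatory Aim 1 tests, control their overall two-sided error at .05 with Holm's procedure, and label comparisons of other between-session activities exploratory. Each deviation measure should be one participant-level mean giving one test, so that the family is fixed at three.

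This takes one or two sentences and no new data or participants. The price is the loss of power in the table above, which the sponsor should weigh across the whole range of adherence effects.

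To protect the outcome that set the sample size, the sponsor could instead test dropout first at .05 and then the adherence measures in a stated order. This also controls the error and costs dropout nothing, but adherence can then be claimed only if dropout succeeds. Whichever rule is chosen should be written down before the outcome data are examined.

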Table 6 shows the projected number of individuals who are expected to be excluded for the reasons listed above, and the number expected to discontinue participation prior to randomization (5%). We have accounted for this in the derivation of our sample as well. We anticipate that a total of 198 women will be deemed appropriate and will agree to randomization. The required sample size of 148 women is therefore feasible given the projections described here.

Table 6: Estimates of eligibility determination prior to randomization

	Projected N(%)
Number (%) consented and enrolled	400
Excluded: untreated sleep disorders	140 (35%)
Excluded insomnia remission	4 (1%)
Excluded: unstable/severe medical or psychiatric condition discovered during assessment	48 (12%)
Number (%) of consented) eligible for randomization	208 (52%)
Withdraw after baseline, prior to randomization	10 (5%)
Number who agree to be randomized	198 (95%)
Number (%) randomized	148 (75%)

3.4c. Randomization: Individuals who complete the study baseline assessment and meet all inclusion/exclusion criteria will be randomly assigned to one of the two intervention groups: ABC-I (n=74), or CBT-I (n=74). [name] will make all final determinations regarding eligibility for randomization with input from the study physicians. Both interventions are described in detail below. Randomization procedures will follow the CONSORT criteria for randomized trials.⁴⁷ Stratified randomization will be used to help insure that ABC-I and CBT-I groups are balanced in baseline severity of sleep problems. Strata will be based on hours of sleep reported on the screening postal survey (>6 hours vs. \leq 6 hours). The number of subjects in each stratum is not expected to be equal, but within each stratum, half will be assigned to each group (ABC-I and CBT-I). This will help to insure balance in baseline severity across the two treatment groups.

[name] (statistician) will generate the stratified randomization sequence. A set of envelopes containing the group assignment will be generated and the data manager ([name]) will store the randomization envelopes in a secure file drawer that only she and [name] can access. Once eligibility is determined, [name] will open the next envelope in sequence within the appropriate stratum.

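### Randomisation is stratified by reported sleep hours, but no planned test uses the stratum and the dropout chi-square is not said to be corrected or uncorrected; the cost is small and conditional, and the remedy is nearly free

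*Combined protocol and SAP*

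**What the plan says.** Section 3.4c, on the stratification: "Strata will be based on hours of sleep reported on the screening postal survey", cut at six hours, with equal allocation to the two arms inside each stratum. The stated purpose is balance in baseline severity of the sleep problem. The split between strata is not given: "The number of subjects in each stratum is not expected to be equal".

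The planned tests are these:

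- **Dropout (3.8c):** a two-by-two chi-square test "of whether dropping out (1=yes 0=no) is independent of treatment group assignment". Continuity correction is not mentioned, here or in the sizing.
- **Adherence in minutes of deviation (3.8c):** "a two group t-test will be used".
- **Aims 2 and 3 (3.8d):** for each sleep outcome, "a 2 (group) by 3 (time) mixed model analysis of variance (ANOVA) will be performed", followed by group-by-time contrasts.

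None of them names the stratum. Section 3.8b discusses stratified randomisation and then says that "covariates may be used to enhance statistical power by reducing error variance", without naming a covariate or committing to one.

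On size, section 3.8c says: "The current study would need 148 subjects (74 per group) to have 80% power", for 22% dropout with ABC-I against 45% with CBT-I.

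**The concern.** When arms are balanced on a factor that predicts the outcome, the true sampling variance of the arm difference falls. A test that ignores the factor still uses the larger, unstratified variance. Its true size then drops below nominal and some power is given up.

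The silence on continuity correction is a second gap. A corrected and an uncorrected chi-square on the same table give different p-values, and stratified or unstratified versions double the choice. Dropout is a primary outcome and it set the sample size, so these choices should not remain open until the data are in hand.

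**Working it through.** **1. Reproduce N = 148.** Inputs from section 3.8c: p1 = 0.22, p2 = 0.45, power 80%. Alpha is not stated for Aim 1; two-sided 0.05 is assumed, and it reproduces the table. With p̄ = 0.335 and d = 0.23:

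n₀ = [1.960·√(2·0.335·0.665) + 0.8416·√(0.22·0.78 + 0.45·0.55)]² / 0.23² = 64.9, so 65 per arm and 130 in total.

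With the continuity correction, n = (n₀/4)·[1 + √(1 + 4/(n₀·d))]² = 73.4, so 74 per arm and 148 in total.

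All 49 cells of Table 11 match the corrected formula exactly, and none matches the uncorrected one. (The text beside the table also prints 178 for this pair of rates; 178 is the 24%/45% cell, and the calculation supports 148.) The correction in the sizing therefore added 148 − 130 = 18 women.

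**2. Unstratified test at 74 per arm, exact binomial enumeration.** Size is at a common rate of 33.5%, power at 22% vs 45%.

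| Analysis test | Size | Power |
|---|---|---|
| Chi-square, uncorrected | 5.0% | 85.3% |
| Chi-square, corrected | 3.2% | 80.5% |

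**3. Effect of the stratum.** The documents give neither the split between strata nor any association between sleep hours and dropout. Assumed: 50:50 or 70:30 strata, one common stratum-dropout odds ratio (OR) in both arms, and overall rates held at 22% and 45% (33.5% in both arms for size).

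With m_k per arm and t_k dropouts in stratum k, the Cochran-Mantel-Haenszel (CMH) statistic is [Σ(a_k − t_k/2)]² / ΣV_k, where a_k is the number of dropouts in one arm and V_k = m_k²·t_k·(2m_k − t_k) / [(2m_k)²·(2m_k − 1)].

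Both tests uncorrected, 50:50 strata (37 per arm in each), enumerated exactly:

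| Assumed OR | Size, unstratified | Power, unstratified | Power, CMH | CMH minus unstratified |
|---|---|---|---|---|
| 1 | 5.0% | 85.3% | 84.9% | −0.3 |
| 1.5 | 4.9% | 85.4% | 85.3% | −0.1 |
| 2 | 4.7% | 85.5% | 85.9% | +0.4 |
| 3 | 4.3% | 86.0% | 87.3% | +1.4 |
| 5 | 3.6% | 86.7% | 89.4% | +2.7 |

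(Differences are taken before rounding.) The size of CMH stays between 4.9% and 5.1% in every row. With 70:30 strata the gains at OR 2, 3 and 5 are about 0.2, 0.8 and 1.8 points.

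**4. Hand check of one row.** At OR 3, 50:50 and an overall null rate of 33.5%, the stratum rates are 21.7% and 45.3%. The mean within-stratum variance is (0.217·0.783 + 0.453·0.547)/2 = 0.209; the pooled variance is 0.335·0.665 = 0.223. The ratio is 0.937, with square root 0.968. The nominal cut-off of 1.960 acts as 1.960/0.968 = 2.02, a two-sided size of 4.3%, as in the table.

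**5. The other tests.** The plan's adherence sizes reproduce. Bedtime: pooled SD √[(36² + 19²)/2] = 28.8 and difference 20 give 33 per arm, 66 in total. Rise time: pooled SD √[(40² + 14²)/2] = 30.0 and difference 30 give 16 per arm, 32 in total. Against 148 randomised there is ample room. The Aims 2 and 3 contrasts are differences between time points, so a stratum effect that is constant over time cancels; only a stratum-by-time effect could matter.

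**The case against.** The case for leaving the plan alone has four parts.

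- **The harm is conditional.** An uncorrected chi-square has nominal size unless sleep hours predict dropout. The stratum was chosen to balance severity, not dropout risk, and the documents show no such association. Up to OR 1.5 stratifying gains nothing. This stands.
- **The planned power is met.** At the planned rates every case above exceeds 80%, and any error is on the conservative side, so there is no added false-positive risk for Aim 1. This stands at the planned rates. The room is limited, though: Table 11 itself asks for 178 at 24% vs 45% and 174 at 22% vs 43%, both above 148.
- **Covariates are already allowed.** Section 3.8b leaves adjustment open. This stands in part: the gap is a lack of pre-specification, not a decision against adjustment.
- **The gain elsewhere is slight.** This stands for adherence and, unless the stratum acts differently over time, for Aims 2 and 3.

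A reader might go further and infer that the primary test runs below 5% and throws power away. The documents do not support that. It would need either a prognostic stratum, which they do not show, or a corrected analysis test, which they do not specify. Nor does the correction in Table 11 cost power; it raised N. And setting 80.5% (corrected, unstratified) beside 87% to 89% (uncorrected, stratified) would credit stratification with a difference that comes mostly from the correction.

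**Conclusion.** The mismatch between design and analysis is real: allocation is stratified and no specified test reflects it. Its cost is modest and conditional, from a 0.3-point loss through stratifying needlessly to a 2.7-point gain at an assumed odds ratio of 5 with equal strata. The unstated continuity correction matters more, at 85.3 − 80.5 = 4.8 power points if the analysis test turned out to be corrected. Neither threatens the stated 80% at the planned dropout rates.

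This is therefore an efficiency and pre-specification point, not a validity problem. The figures rest on the assumed stratum split, a common odds ratio in both arms and two-sided alpha of 0.05. The pre-specification argument holds even if the stratum proves unrelated to dropout.

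**What to change.** - **Dropout:** make the primary test the Cochran-Mantel-Haenszel test stratified by the randomisation stratum, stated to be without continuity correction, and report the stratum-weighted risk difference with its 95% CI.
- **Adherence:** replace the t-test by a linear model with arm and stratum.
- **Aims 2 and 3:** add the stratum and its interaction with time to the models. This is for consistency; little gain is expected.
- **Section 3.8b:** name the stratum as a committed covariate.

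The cost is about one sentence per analysis, with no new data, since the stratum must be known before each woman is randomised. The statistical downside for the dropout test is about 0.3 power points if the stratum is not prognostic. The sample size need not change.
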